It has been our experience that some patients who report a recent suicide attempt or moderate suicidal ideation who are currently being managed by a mental health provider are able to successfully participate in surveys and interviews. Research staff will explicitly discuss the potential risks inherent in research involvement and the participant's concerns about involvement with those participants who endorse mild or moderate suicide ideation. This information, in combination with the patient's medical records and self-report, will help the research staff to make his/her decision regarding study eligibility. If any of these determinations are unclear, he/she will consult with the supervising psychologist ([name]) or psychiatrist ([name]), both of whom have research and clinical expertise in suicide risk management, for a second opinion. Participants who report acute suicidality will not continue with assessment procedures and will be referred to same-day care through either a Primary Care-based Psychiatrist or the VAAAHS emergency department, in compliance with human subject protections procedures, or will be referred to the same locations or to specialty mental health if the treatment needs are non-urgent. Those participants in the trial who report acute suicidality at a 3- or 6- or 12-month follow-up assessment will be assessed for imminent risk and connected to the appropriate type of mental health services. Research staff will attempt to contact at least three times within 72 hours participants who flag for risk (suicide or opioid) in with mailed follow-up assessment. Mailed follow-up assessments will include an insert that alerts the participant that this survey is not a way to reach out for help regarding suicidal ideation or thoughts. It will include the Veterans Crisis Line number and inform the participant that if they indicate suicidal thoughts or ideation that the research staff will follow-up once the survey is received.

In the course of study participation, including the assessments, intervention, or EUC activities, it may be determined that a participant is at acute risk for serious self-harm related to their opioid use. Study staff have been trained to include in the exclusions of confidentiality, self-harm not only in terms of suicide but also related to participant's opioid prescription. Participants will be notified that research staff may discover opioid self-harm risk from the survey, intervention session or general discussion with the participant. When this risk arises, study staff will discuss this risk with the patient and discuss that the provider will be informed. The participant will be given the option to disclose this to their provider, with the study staff in the room, when possible. Study staff will notify the participant's prescriber in the situation where the participant does not, or the provider is not available, based on protocols that were designed in consultation with opioid prescribers through focus groups and primary care staff meetings. The discussion between study staff and provider will only discuss the relevant information (e.g., mentioned use of cocaine, endorsed using heroin, etc.), but will not make any clinical conclusions or suggestions. Study staff will also make additional referrals as needed. During data analysis, we examine any impact through a sensitivity analysis. Additionally, we will notify all participants' prescribers that the participant is at risk for overdose due to their medication regimen and/or OA use behaviors. The notification will include the fact that we will have discussed this risk with the patient. This will be done for both intervention and control participants to avoid potential differential effects on the measurement.

Drs. [name], [name], and [name] will be responsible for providing training to all research staff working with participants at the study site with regard to procedures for managing issues that could arise given the patient population, including potential crisis situations and/or adverse events. Given the population under study, it is expected that participants may report current suicidality. Specifically, this training will include information regarding evaluating warning signs of acute suicidal ideation, planning, or intent, and means of addressing such issues. Research staff will be trained in crisis procedures including limits of confidentiality, how to liaison with study site staff (i.e., treatment providers, crisis management) to arrange for an assessment and potential admission for inpatient care, and circumstances in which it may be necessary to notify authorities regarding intent to harm self or others. The crisis procedures also will include immediately paging Drs. [name] or other clinical staff for consultation and conference call discussions with other investigators as necessary.

Additionally, research staff will be trained to use certain strategies should participants express emotional distress such as: intervening early, avoiding blame, increasing empathy, processing in a non-blaming non-confrontational manner, and taking a break in the session if necessary. The training manual will contain written procedures for dealing with such situations and will include a detailed, ordered list of phone numbers (i.e., home, work, cell, pager) to facilitate immediate contact with investigators.

For individuals that trigger the need for a suicide assessment, research staff will inquire about plan, severity, and risk factors. Drs. [name], [name], or [name] will be contacted for individuals that are at high risk (i.e. distinct and/or immediate plan to harm oneself). Staff will consult with the supervising psychologist ([name]) or psychiatrist ([name]), both of whom have expertise in assessing suicide risk. Drs. [name], or [name] will make a decision about appropriate next steps, including the need for emergency or follow-up evaluation, requesting the participant to contact a family member or friend, contacting a facility/hospital staff member (i.e., psychiatrist on call, participant's provider) before the study staff member leaves the location, performing a warm handoff with the Veterans Crisis Line, contacting local authorities, etc. If Drs. [name] or [name] indicate the level of risk suggests the need for a professional or emergency evaluation, the study staff member will assist in facilitating the next step. All participants will be given mental health referral information.

Study Specific Plan for Reporting Adverse or Other Reportable Events or Information

Given the characteristics of the study population (participants prescribed high doses of opioid pain medication), we will create a study specific adverse event reporting plan. We will report all AEs that are **unexpected and directly related** to the study (except as noted in the first row of the table below). "Unexpected" means that the event has not been addressed or described in the informed consent document, protocol, data and safety monitoring plan, and/or is not a characteristic of the study population. "Related" means events that are caused by the research itself, not the disease or population under study. Unexpected events that are not directly related to the study will not be reported (see examples in table), with the exception of participant death.

The person responsible for reporting adverse events will be [name]. In addition, [name] will ensure that all relevant VA IRB policies, procedures and stipulations are being followed. [name] will also be responsible for ensuring that other investigators and project staff adhere to the VA IRB policies including: (1) All participants will understand, agree to, and sign a written consent form before participating; (2) Strict adherence to a participant's right to withdraw or refuse to answer questions will be maintained; (3) The assessments will be completely confidential and no names will be associated with the assessment data; (4) Consent forms and identifying information will be kept separately from the actual participant data; (5) All identifying information will be kept locked at all times and computer files will have restricted access; (6) Participants will be informed in writing in the consent form how to contact the PI with any questions and/or concerns. The study coordinator will compile information of adverse events, UPRs, and SAEs on an ongoing basis. On a quarterly basis during the period of active recruitment and follow-up, the coordinator will report this information to the PI and the other study investigators at study meetings meant to monitor study progress. In advance of this meeting, the PI will review these data with the coordinator so that any additional information needed to evaluate the monitoring plan can be obtained prior to the meeting.

The table below is included to outline what are expected events specific to our study:

Type of Event	Examples	Reporting Timeframe
Expected and Study-Related Serious Adverse Events	
Hospitalization as a direct result of study interaction resulting from report of self-harm thoughts or behaviors (e.g., acute opioid risk, or suicidal).	Reported in accordance with IRB guidelines

Expected and Study-Related Adverse Events	
 Participants reporting self-harm thoughts or behaviors Breach of confidentiality associated with reporting self-harm to agency staff, appropriate authorities, and/or mental health personnel. Discomfort associated with answering survey questions/discussing intervention topics. 	Not reported to IRB
Expected and Not Study-Related Adverse Events and Serious Adverse Events	
 Emergency room visit related to self-harm or substance use/overdose Hospitalization for suicidal thoughts or substance use/overdose Social or psychological trauma related to substance use 	Not reported to the IRB
Expected protocol deviations/exceptions	
 Missed appointments and/or sessions. Breach of confidentiality associated with reporting suspected abuse to Child or Elderly Protective Services. 	Not reported to IRB
Unanticipated Problem Involving Risks to subjects or Others (UAP) – Serious and Non-Serious		Reported in accordance with IRB guidelines

6. Inclusion of Women, Minorities, and Children

Inclusion of Women

Of the 450 Veterans recruited to participate in this study, we expect that about 5.5% (N = 24) will be women, based on the overall prevalence of female gender among patients treated with opioids in primary care at the VAMC. Pregnant women will not be included in the study.

Inclusion of Minorities

Of the 450 Veterans recruited into this study, we expect that the sample will consist of 1.5% Hispanic or Latino/a Veterans. Regarding race, we expect that 9.8% will be Black or African American, 88.5% White, 0.8% American Indian or Alaskan Native, 0.5% Asian, and 0.4% Native Hawaiian or Other Pacific Islander.

Inclusion of Children

This project will not include children. Individuals age 17 years old and under will be excluded due to the study focus of pain management in VHA primary care among Veterans. These veterans will be at least 18 years old. Notably, pain conditions are relatively uncommon among children as compared to adults; however, due to biological, psychosocial, and developmental differences between these age cohorts, even those children with

pain conditions likely require dissimilar approaches to pain management and adverse event risk management compared to adults. Based on these differences, a separate study would be required to appropriately examine opioid safety among children and adolescents with pain conditions.

LITERATURE CITED

1. The Management of Opioid Therapy for Chronic Pain Working Group. VA/DoD Clinical Practice Guideline: Management of Opioid Therapy for Chronic Pain: Department of Veterans Affairs & Department of Defense; 2010.

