Patient safety. During the study, we may determine that a participant is at serious, imminent risk for serious self-harm related to their OA use. Study staff will notify the participant's prescriber in this situation and will make additional referrals to mental health or emergency services as needed. These participants will be withdrawn from the study and will not be included in analysis (see section on Feedback to Providers on page 11). For non-OA related risks, such as suicidal ideation, staff will discuss the risks of participation with the patient and review screening responses and the medical chart (e.g., for ongoing mental health care) to decide study eligibility. If any of these determinations are unclear, staff will consult with the supervising psychologist ([name]) or psychiatrist ([name]), both of whom have expertise in assessing suicide risk. Participants who report acute suicidality will be able to continue with study procedures at a later time and will be referred to same-day care through either a PC-MHI-based Psychiatrist or the ED. If treatment needs are not urgent, the participant will be referred to specialty mental health and continue with study protocols. Those participants in the trial who report suicidality at a 3-, 6-, or 12-month follow-up assessment will be connected to the appropriate services (outlined in the Safety Monitoring Plan section on page 21).

Usual care, intervention, and EUC procedures. Both intervention and EUC participants will receive the Long-Term OA informed consent and will review the VHA's "Taking Opioids Responsibly for Your Safety and the Safety of Others" pamphlet with a study therapist (usual care). The study therapists will coordinate with the patients' prescribing physicians to document this process if a participant had not already provided informed consent. For the intervention condition, the informed consent process will lead to a tailored, ME-adherent discussion of reducing the risks of OAs, but for the EUC condition, the informed consent process will be followed by psychoeducation on topics related to pain management, will not be tailored, will not include elements of ME, and will not include content on overdose risk behaviors. If a patient expresses a wish to change their OA regimen after any of the intervention or control content, the study therapist will assist the patient in arranging an appointment with their prescriber.

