The 3-, 6-, and 12-month assessments will occur in at the Ann Arbor VAMC. In cases where this is not feasible for the participant, the research staff will arrange to meet the participant at a convenient location in the community (e.g. participant home, library), conduct the assessment by phone, or mail the assessment to participants to complete and return to the research team. In cases where the follow-up assessments are conducted via U.S. mail and a participant endorses risk (suicide or opioid, according to our protocol), research staff will make at least three attempts to reach the participant within 72 hours of receiving the survey to further assess level of risk and/or answer questions. Every mailed survey packet may include the resource brochure which includes national suicide hotlines, VA Crisis Line and mental health services. Privacy during assessments will be achieved by making sure no one can overhear the conversation. If applicable, research staff will ask the research subject to have others leave the room during interviews. The research assistant conducting follow-up will be blind to group status. Based on our prior research,^{68,69,79} we conservatively estimate that 80% of participants will be interviewed at follow-up. Techniques to ensure high retention include: gathering extensive tracking information, using reminder letters as well as contacting participants by phone, and scheduling follow-up interviews at the participants' convenience. Participants will be contacted two weeks prior to the assessment due date to schedule an appointment. Study staff will monitor primary care appointment logs for participants who have not responded to letter and phone contact and non-obtrusively approach patients in waiting areas. The 3-, 6-, and 12-month follow-up assessments will take approximately one hour to complete and participants will be given \$30 (+\$5 for a voluntary UDS) for each plus an additional \$10 to assist with travel expenses.

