Medical Chart and Administrative Data Extraction. Data will be extracted from the CDW Production Domains, and CDW MCA (formerly DSS) NDE, MedSAS Files including VetsNet Files and CAPRI/VistAWeb datasets as well as the Opioid Therapy Risk Report (OTRR). The OTRR allows VA providers to efficiently monitor clinical data related to opioid pain treatment within the electronic medical record (EMR). The OTRR provides a list of patients on long-term opioid therapy with upcoming primary care appointments, along with related opioid risk factors. Opioid pain medications will be requested from CDW MCA NDE pharmacy data. Dates of fills, day supply, prescribing physician, total quantity and dosing and schedule instructions will also be used. We will collect basic demographic information (name, birthdate/age, race, social security number), OEF/OIF/OND service, diagnosis (e.g., terminal cancer), clinic appointment information (date of appointment, type of appointment, etc.), and basic contact information (address, phone numbers) for those receiving long-term OA therapy treatment. These data will be extracted from the staff, patient, appointment, inpatient, outpatient and pharmacy CDW Production Domains, MedSAS Files and/or the OTRR. CAPRI/VistAWeb will be used to check for external appointments. Research staff will confirm upcoming appointment and eligibility. Access to real SSN data is needed in order to link the administrative data from the MedSAS datasets, CDW and OTRR to data from chart reviews. In addition to OA regimen, data will be extracted over follow-up to assess VHA service use, diagnoses, mental health assessments, other medication use, and mortality (from the Beneficiary Identification Records Locator Subsystem of Vital Status; mortality will also be measured by information that comes from the contacts nominated by that participant or records databases and obituary listings). VHA service use, diagnoses, mental health assessments, and other medication use will be extracted from CDW Production Domains, MedSAS files and CAPRI/VistAWeb. We will also examine the chart for information related to the prescriber notification in order to better understand the impact of the notification process. We will use both VINCI and our local VA server for the administrative data extraction of potential patients that fit our eligibility criteria. The use of both storage options will increase our ability to find potential patients in a timely manner and avoid delays due to occasional problems with the transfer of data from VINCI to our local VA server. The OTRR will be saved to our local VA server.

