Demographics Information on participants' race, gender, sexual orientation, OEF/OIF/OND status (MSI), marital status, employment status, income, and education will be collected. Contact information and housing status, address, phone number, e-mail (if applicable) and type of living arrangement will also be collected.

Analysis plan. The project's data management and analysis will be supervised by [name], who received advanced biostatistics training during her Ph.D. in public health. Tests for linearity, independence, missingness, and distributional assumptions will be conducted on key variables. Distributions will guide modeling decisions and normalizing transformations will be used when appropriate.

Although we expect that randomization will balance the groups, we will validate randomization by comparing groups on key variables potentially related to outcomes. If we identify significant group differences, we will adjust for these variables in models. The EUC condition will be designed to be equal-attention, but we will examine potential associations of the outcomes with length of session in sensitivity models.

Mixed effects regression models (described below) will allow the use of data from all participants, including those with incomplete follow-up, and provides unbiased parameter estimates under the missing-at-random assumption.¹⁰² If the missing-at-random assumption is untenable, we will handle missing data with a pattern mixture model. Where we have missing data on individual variables for more than 15% of observations, we will impute using SAS PROC MI and PROC MIANALYZE to combine the results of PROC MI.

Generalized linear models (GLMs) and generalized linear mixed-effects models (GLMMs). We will assess treatment effects by using GLMs to examine differences between the intervention and EUC groups at specific assessment waves and GLMMs to examine the primary dependent measures over the study period as a whole. GLMMs have the advantage of: 1) adjusting variances for correlated data (i.e., repeated measures); 2) allowing time-varying independent variables; and 3) allowing subject-specific inferences. The link function for GLMs and GLMMs will be based on the distribution for each outcome. We will use procedures SAS PROC MIXED for continuous variables and PROC GLIMMIX for dichotomous and count data.

Aim-specific analyses. All hypotheses will be planned a priori. All analyses will use two-sided tests.

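### The Patient safety section drops participants found at serious opioid-related risk from the analysis without limiting this to the time before randomisation

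*Combined protocol and SAP*

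**What the plan says.** - **Patient safety** (Research Design and Methods): "During the study, we may determine that a participant is at serious, imminent risk for serious self-harm related to their OA use". The prescriber is notified and referrals are made as needed. Then: "These participants will be withdrawn from the study and will not be included in analysis". The sentence refers the reader to the section on feedback to prescribers.
- **Exclusion criteria**: criterion 6, acute opioid-related self-harm risk that needs immediate treatment, points forward to the Patient safety section.
- **Randomization**: allocation follows the baseline assessment. The sessions and the 3-, 6- and 12-month assessments therefore come after it.
- **Safety Monitoring Plan**: "In the course of study participation, including the assessments, intervention, or EUC activities, it may be determined that a participant is at acute risk". The response given is discussion, prescriber notification and referral, followed by "During data analysis, we examine any impact through a sensitivity analysis". Neither withdrawal nor exclusion from analysis is mentioned.
- **Analysis plan**: "Mixed effects regression models (described below) will allow the use of data from all participants, including those with incomplete follow-up".
- **Feedback to prescribers**: the situations that merit notification include use alongside heroin, cocaine or benzodiazepines, and snorting or injecting. The list is open-ended and may change. Serious, imminent risk is expected to be fairly uncommon.
- **Measures, Overdose Risk Behaviors (ORB)**: the Aim 1 count includes combining opioids with other substances and route of use.

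**The concern.** Taking randomised people out of the analysis because of something observed after allocation gives up the protection of randomisation. It is worse when the reason for removal is close to the outcome. Here the trigger is risky opioid use and the Aim 1 outcome is a count of risky opioid-use behaviours.

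If the two arms detect such cases at different rates, the ORB comparison is distorted. The documents give some reason to consider this. The intervention session asks about drug use and overdose risk behaviours, while the enhanced usual care (EUC) session leaves that content out. The baseline and follow-up surveys are the same in both arms.

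The rule also removes these people from the analyses of dose, medication possession ratio, overdose and emergency visits, although pharmacy and chart data would usually still exist for them. No section defines the analysis set, so two analysts could follow this document and analyse different people.

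**Working it through.** **1. Can the rule reach randomised participants?**

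The rule applies during the study. Allocation follows baseline, and the Safety Monitoring Plan expects such risk to be found in assessments, intervention sessions or EUC activities. Sessions and follow-up assessments take place after randomisation. No section confines the rule to the period before it, so as written it can reach randomised participants.

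**2. The plan's own power figures (background)**

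- Analysed number: 450 × 0.80 = 360, or 180 per arm.
- Standardised effect 0.30, two-sided 0.05: power 0.81.
- Poisson mean 1.9, incidence rate ratio (IRR) 0.80: Wald variance 1/(180 × 1.9) + 1/(180 × 1.52) gives 0.79; a null-variance version gives 0.82.

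The stated 80% is reproduced. If 5% are excluded (171 per arm), power is 0.79 and 0.76 (Wald). Lost power is not the main issue.

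**3. Distortion of Aim 1 when there is no true effect**

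From the documents: ORB mean m = 1.9 and SD 2.0 (Measures), and 180 per arm (Power analysis). Assumed: withdrawal fractions e_I (intervention) and e_C (EUC), the flagging rule, and a correlation r of 0.5 to 0.7 between ORB at the session and at follow-up.

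If flagged people have mean h at the session, their expected follow-up mean is approximately y = m + r(h − m). Then

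IRR = [(m − e_I·y)/(1 − e_I)] ÷ [(m − e_C·y)/(1 − e_C)].

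A negative binomial with this mean and SD has P(≥1) = 72.2% and P(≥4) = 17.5%. The values of h are:

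- anyone with at least 1 behaviour equally likely to be flagged: 1.9/0.722 = 2.63;
- flagging proportional to the count: (2.0² + 1.9²)/1.9 = 4.01;
- flags confined to 4 or more behaviours: 5.37.

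Example with proportional flagging, r = 0.5, 5% v 2%: y = 1.9 + 0.5 × (4.01 − 1.9) = 2.95. The intervention mean is (1.9 − 0.05 × 2.95)/0.95 = 1.845 and the EUC mean is (1.9 − 0.02 × 2.95)/0.98 = 1.879. The IRR is 1.845/1.879 = 0.982.

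A simulation of 2 million correlated pairs agrees with this formula to within about 0.003 and gives (r = 0.5 / r = 0.7, type I error in brackets):

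| Withdrawn, intervention v EUC | At least 1 behaviour | Proportional to count | 4 or more only |
|---|---|---|---|
| 5% v 5% | 1.00 (5.0%) | 1.00 (5.0%) | 1.00 (5.0%) |
| 3% v 1.5% | 0.997 / 0.996 (5.0%) | 0.991 / 0.988 (5.1%) | 0.986 / 0.980 (5.2–5.4%) |
| 5% v 2% | 0.993 / 0.991 (5.0–5.1%) | 0.982 / 0.975 (5.3–5.6%) | 0.971 / 0.958 (5.8–6.6%) |
| 10% v 3% | 0.982 / 0.977 (5.3–5.5%) | 0.955 / 0.937 (6.8–8.7%) | 0.927 / 0.895 (10.0–15.9%) |

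Reversing the imbalance (2% v 5%) gives 1.01 to 1.04.

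**4. What keeping everyone in the analysis would leave**

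At 5% v 2%, using baseline ORB as a covariate or auxiliary variable (assumed correlation of 0.6 to 0.8 with the session value):

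- no later ORB obtained: 0.97 to 1.00;
- half obtained: 0.99 to 1.00;
- all obtained: 1.00.

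The full mixed model and the pattern-mixture model were not simulated.

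**The case against.** **The sentence may concern screening only.** Criterion 6 points to this section. The next sentence in the section, on risks not related to opioids, speaks of deciding eligibility, and a later one turns separately to people already in the trial. The screening survey comes after consent, so a consented person could be withdrawn without ever having been randomised. This stands as a possible reading. The wording about the study period and the Safety Monitoring Plan count against it, and the text does not settle the matter.

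**The Analysis plan does not define an analysis set.** It describes what mixed models can use. That is correct, so the tension there is one of fit and not a flat contradiction. The tension with the Safety Monitoring Plan is by implication, because its sensitivity analysis could also mean adding withdrawn people back.

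**Stronger readings that the documents do not support.**

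- *Other sections contradict the rule.* For mailed surveys on which "a participant endorses risk (suicide or opioid, according to our protocol), research staff will make at least three attempts to reach the participant", and in the matching Safety Monitoring Plan sentence, "Research staff will attempt to contact at least three times within 72 hours participants who flag for risk (suicide or opioid", the contact serves to assess risk further and comes before any determination. The chart review, "We will also examine the chart for information related to the prescriber notification in order to better understand the impact of the notification process", concerns a process that includes a notification made for every participant. These sections are silent on withdrawal and do not conflict with the rule.
- *Everyone on the notification list is withdrawn.* No section says so. Serious, imminent risk is a narrower threshold.
- *Detection differs by arm.* This is an inference from session content. Both arms complete the same baseline before allocation, and the research assistant at follow-up is blind.

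**Conclusion.** The point holds as a should-fix. As written, the rule permits an outcome-related exclusion after randomisation, and the document does not say clearly who is analysed. Confidence in that reading of the text is high, subject to the possible screening-stage interpretation.

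Confidence in the size is low. No rate and no arm difference is documented. Under the assumed 5% v 2%, the apparent IRR is 0.96 to 0.99 with type I error of about 5% to 7%. Equal withdrawal with no true effect gives no distortion, and the direction is not settled. A reader might infer a serious threat to Aim 1 from the 10% to 16% type I error in the last row of the table. That needs both a 10% v 3% split and flags confined to high scorers, and nothing in the documents supports either.

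The case for change rests on the unclear analysis set and the needless loss of record-based outcomes, not on a demonstrated large bias.

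**What to change.** 1. In Patient safety, remove the clause on exclusion from analysis for randomised participants. People found at risk before randomisation are simply not randomised.
2. State that every randomised participant is analysed in the assigned arm, using all data collected before withdrawal and, where consent allows, the pharmacy, chart and mortality data already planned under Medical Chart and Administrative Data Extraction.
3. Record each flag with arm and date. Define the sensitivity analysis in the Safety Monitoring Plan as the one that leaves flagged participants out.
4. Treat ORB waves not observed after withdrawal as missing under the planned mixed model.
5. Add a pattern-mixture sensitivity analysis and, for participants with no follow-up ORB, imputation using baseline ORB. Both would be new. The current plan uses a pattern-mixture model only as a replacement if missing-at-random is untenable, and imputes only where a variable is missing for more than 15% of observations. Baseline ORB should be a covariate or auxiliary variable and not a response, because its recall period differs from that of the follow-ups.
6. Reconcile Patient safety, Analysis plan and Safety Monitoring Plan.

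The cost is wording in three sections, one dated flag variable and two added analyses; the record extraction is already planned. The downside is that Aim 1 then relies on missing-at-random for withdrawn participants without later ORB. At 5% v 2% the IRR moves only from 0.96–0.99 to 0.97–1.00 if no later ORB is obtained. Whether participation should end for safety is a separate decision, on which no view is given.
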